- Endocrine/rheumatologic diseases: hypothyroidism, diabetes mellitus and rheumatoid arthritis.
- Number of calcifications
- Size of calcifications: mm
- Previous treatments: Yes/ No
- Location of calcification: Supraspinatus, subscapularis, and infraspinatus.
- ROM: Flexion, abduction, and external and internal rotation (°).

- **Visual analgesic scale (VAS):** initial, at 1, 3 and 6 months.

- **Latineen test: initial, at 1, 3 and 6 months of each test variable and final score.**

Correlation of VAS levels and Latineen test: (14)

VAS of 0 - 2.5 → IL = 6 VAS of 2.5-5 → IL=10 VAS of 5-7.5 → IL 13 VAS of 7.5-10 → IL =14

- **Patient Global Impression of Improvement Scale (PGI-I)**
- **Global improvement impression scale (CGI - GI)**

Sample size

Accepting an alpha of 0.05 and a beta of 0.2 in a bilateral contrast, 28 subjects in each arm are required to detect a difference equal to or greater than 3 units on the VAS scale. A standard deviation of 5 is assumed. A loss-to-follow-up rate of 20% has been estimated.

Work plan

The protocol carried out was as follows:

1st Phase : in this first phase, patients will be collected according to the criteria set out above for a period of **12 months**. During this time, the patients will be explained the two possible treatments to be received and after signing the appropriate informed consent, **they will be divided into groups according to treatment (ESWT vs US-PICT) stratifying according to the Bianchi Martinoli classification: (I/II or III)**. The decision for each

treatment will be made randomly, **dividing the patients in a 1:1 ratio** according to whether they come to the initial consultation and the previous patient has received one or the other treatment.

The variables indicated above and in the table of variables will be collected from these patients.

	ESWT	US-PICT
Type I	14n	14n
Type II/III	14n	14n

In relation to **ESWT**, these will be given using a **15 mm transmitter in continuous mode with pressure at 3 bar, frequency 12Hz and 3000 impacts**. The number of sessions will be between 4 - 8 according to the patient's clinical condition with a rest between sessions of 5 to 10 days.

US-PICT will be performed with 1 session in which the following actions will be performed:

- First, a **suprascapular nerve block** will be performed with corticosteroid and anesthetic (3 ml of bupivacaine) in an ultrasound-guided manner.

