- Then **the calcification will be infiltrated** with 5 ml of local lidocaine and preloaded physiological saline solution under ultrasound guidance.
- Finally, **repeated suctioning** with physiological saline will be performed to extract the calcium in an echoguided manner.

The inclusion of patients in the study will be carried out by [name]. The barbotomy technique will be performed jointly by [name], [name] and [name]. The ESWT technique will be performed by Fst. [name].

2nd Phase: Subsequently, 3 revisions will be carried out. One at 1 month, 3 months and another at 6 months after the end of therapy. In these, the variables will be taken again as indicated in the table of variables.

Initial consultation	1 month	3 month	6 month
Age Gender Type of therapy Diseases Number of calcifications Size Previous treatment Location ROM (measurement with goniometer) VAS _{in} Latineen Test	ROM (measurement with goniometer)	ROM (measurement with goniometer)	ROM (measurement with goniometer) VAS _{6m} Latineen Test PGI – I CGI - GI

Table of variables

3rd Phase: The information collected will be synthesized and entered into the SPSS program to obtain the results. For these the following actions will be carried out:

[figure not shown]
- For an independent data design:
 - 2 groups: Student's t-test or Mann-Whitney U-test.
 - More than 2 groups: Analysis of variance or Kruskal-Wallis "H" test.
- For a paired data design:
 - 2 groups: Student's t-test for paired data or Wilcoxon test.
 - More than two groups: Analysis of variance for repeated measures or Friedman's test.

A new variable VAS difference (VASDIF) will be created later, with the data obtained, according to the following formula in order to evaluate the variation with the initial VAS levels.

[figure not shown]
$$\text{VAS}_{\text{in}} - \text{VAS}_{\text{xm}} = \text{VASDIF}_{\text{xm}}$$

Main variables: VAS, Test de Latineen y variables, PGI y CGI.
 Variable agrupadora: ESWT Vs US-PICT

Type I calcifications

Type II/III calcifications

All contrasts will be bilateral and those where $P < 0.05$ will be considered significant. Data will be collected, processed and analyzed with SPSS v.21 statistical software.

Limitations of the study

In order to be able to carry out the following study, the following limitations can be found.

1. Poor adherence to the study by the patients causing losses.
2. Increased waiting times due to ESWT saturation.

Ethical aspects

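### The per-visit tests on VASDIF leave out every patient without a VAS at that visit, and the plan expects 20% loss but has no rule for it

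*Combined protocol and SAP*

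**What the plan says.** The main objective (section 3) compares mean VAS differences between US-PICT and ESWT at 1, 3 and 6 months, by calcification type. In the 3rd Phase of the Work plan, VASDIF for a given month is the initial VAS minus the VAS at that month.

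For independent data the 3rd Phase lists "2 groups: Student's t-test or Mann-Whitney U-test". For paired data it lists "More than two groups: Analysis of variance for repeated measures or" Friedman's test.

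On losses, the Sample size paragraph says "A loss-to-follow-up rate of 20% has been estimated", and the first item under Limitations of the study is "Poor adherence to the study by the patients causing losses". The 20% is not split by arm, visit or reason. The readable text gives no analysis population, missing-data rule, imputation, likelihood-based model or sensitivity analysis.

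**The concern.** VASDIF at month x is undefined when the VAS at month x is missing, so a t-test or Mann-Whitney test on it can use only patients who attended that visit. The plan does not say this in words; it follows from the definition and from the absence of any other rule. The repeated-measures options are listed for paired data, not for the between-arm contrast, and in standard form they also need complete rows.

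The 6-month comparison then describes the patients who stayed rather than those randomised. VAS values collected at 1 and 3 months from patients who later leave are ignored, although they show how those patients were doing. If the leavers differ from the stayers, and differ more in one arm than in the other, the arm contrast is shifted and the nominal 5% error rate is not kept.

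**Working it through.** **Inputs from the documents.** Two-sided alpha 0.05, beta 0.2, 28 per arm ("Accepting an alpha of 0.05 and a beta of 0.2 in a bilateral contrast, 28 subjects in each arm are required"); target difference 3 ("to detect a difference equal to or greater than 3 units on the VAS scale"); SD 5 ("A standard deviation of 5 is assumed"); 20% loss; allocation 1:1; 14 per type-by-arm cell (table in the 1st Phase).

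**Inputs that are assumptions.** The split of loss by arm, its mechanism, the between-visit correlation (0.5 or 0.7), and an alternative SD of 2.5.

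**Step 1. The plan's figure.** For two independent arms, n = 2 × (1.960 + 0.842)² × 5² / 3² = 43.6, so 44 per arm, or 44/0.8 = 55 with loss. The stated 28 is not reproduced. Half that formula gives 21.8, rounded to 22, and 22/0.8 = 27.5, rounded to 28; but that is the one-sample or paired form. This is a separate matter. Below, 28 per arm and 14 per cell are taken as enrolled.

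**Step 2. Who is left.** 28 × 0.8 = 22.4 per arm and 14 × 0.8 = 11.2 per cell. About 5.6 per arm, or 2.8 per cell, drop out of the 6-month test if they leave before that visit.

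**Step 3. When this biases the contrast.** In each arm, the shift is the mean among stayers minus the mean among all randomised. The bias is the shift in one arm minus the shift in the other, so equal shifts cancel. An upper bound takes the poorest responders as the ones who leave: shift = SD × φ(z_q)/(1 − q), with q the proportion lost.

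| Loss by arm (20% overall) | Bias in SD | At SD 5 | At SD 2.5 |
|---|---|---|---|
| 20% v 20% | 0 | 0 | 0 |
| 25% v 15% | 0.15 | 0.75 | 0.37 |
| 30% v 10% | 0.30 | 1.5 | 0.75 |
| 40% v 0% | 0.64 | 3.2 | 1.6 |

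**Step 4. Softer loss, simulated.** 28 per arm, no true difference, three correlated change scores. In one arm, loss is logistic in the change score (20% at the mean, slope 1.5 per SD, about 27% overall). In the other arm it is 10% at random, except in the third row. SD 2.5, correlations 0.5 and 0.7:

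| Loss pattern | Observed-case bias at 6 months (points) | After using 1- and 3-month values |
|---|---|---|
| After month 3, poor responders leave | 0.37 / 0.52 | within 0.05 of zero |
| After month 3, good responders leave | −0.36 to −0.51 | (not tabulated) |
| Same outcome-related loss in both arms (27% each) | 0.00 to 0.01 | (not needed) |
| Before month 1, poor responders leave | 0.37 / 0.53 | unchanged |

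In the first row the t-test's type I error is about 0.07 to 0.11 at 28 per arm. At 14 per arm the bias is similar and the type I error is 0.06 to 0.08. In the third row it is about 0.05. At SD 5 the first-row bias is 0.73 / 1.03. Standard errors are similar (0.73 for the likelihood estimate, 0.74 observed-case, at SD 2.5 and correlation 0.7).

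**Step 5. Loss on the unseen 6-month value.** With 30% v 10% loss, correlation 0.7 and slopes of 1 to 2 per SD in the higher-loss arm only:

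- Loss driven by the 3-month value: bias of 0.17 to 0.26 SD falls to about 0.
- Loss driven by the 6-month value: bias of 0.25 to 0.38 SD (type I error 0.13 to 0.26) falls only to 0.14 to 0.23 SD.

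Equal loss rates do not guarantee safety. At 20% v 20%, with poor responders leaving one arm only, loss driven by the 6-month value gives a bias of 0.17 to 0.26 SD and a type I error of 0.09 to 0.14.

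**The case against.** The strongest reply is that nothing in the documents shows harmful loss. They give one overall rate, and 20% loss does not itself bias a between-arm contrast: loss unrelated to outcome, or the same outcome-related loss in both arms, gives a bias of about zero. This stands, and the point is therefore conditional.

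A reader might infer that ESWT will lose more patients, since it takes 4 to 8 sessions against one, and so will look better than it is. The documents do not support this. The reviews are timed from the end of therapy, so session burden is over before month 1 and gives no particular reason for loss after month 3. The background calls the disease self-limited, so recovered patients may equally stop attending, and the bias then has the opposite sign.

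A reader might also infer that a mixed model removes the problem. The near-zero bias in Step 4 arises because loss was generated from the observed 3-month value, the mechanism such a model corrects. It corrects only in part when loss follows the unseen 6-month value, and not at all for patients with no follow-up VAS.

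The larger figures rest on SD 5, which is hard to reconcile with a 0 to 10 scale. The quoted line is also a generic menu of tests beside a figure that was not extracted. The gap is the missing rule for lost patients rather than the choice of a t-test.

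**Conclusion.** The point holds in conditional form. The listed between-arm tests use only patients with a VAS at the visit in question, the plan expects 20% loss, and the readable text does nothing about it. If loss is related to outcome and differs between arms in rate or mechanism, the 6-month contrast is biased.

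Direction and size cannot be known from the documents. The illustrative 0.4 to 0.5 points at SD 2.5 is about 12% to 17% of the 3-point target (0.37/3 and 0.52/3). It rests on the assumed loss pattern, correlation and SD. A likelihood-based repeated-measures analysis gives similar precision, uses data the plan already lists, and does not require leaving to be unrelated to earlier observed VAS. It is a cheap improvement that lowers a foreseeable risk; it does not correct a demonstrated bias.

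**What to change.** In the 3rd Phase, make the main VAS analysis a linear mixed model for repeated measures:

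- **Model:** VASDIF at 1, 3 and 6 months, with allocated arm, visit, arm-by-visit and unstructured covariance.
- **Patients:** everyone with at least one follow-up VAS.
- **Strata:** fit it within Type I and within Type II/III, as the main objective requires, and also pooled with calcification type in the model. Read the 1-, 3- and 6-month contrasts from it.
- **Sensitivity:** keep the per-visit t-test or Mann-Whitney test. Add a simple analysis for loss that depends on unseen outcomes, covering patients with no follow-up VAS. For example, shift the missing values in each arm over a stated range δ; at 20% missing, an arm mean moves by 0.2 × δ.
- **Reporting:** losses by arm and visit, with reasons where known.

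First confirm that VAS is recorded at 1 and 3 months. The list of variables and the main objective say so, but the table of variables in the 2nd Phase, as extracted, shows follow-up VAS only at 6 months. That may be an extraction fault. If it is not, the model has no earlier values to draw on.

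The cost is analysis wording and a few lines of syntax in the planned SPSS v.21 (MIXED), with no extra visits and no data beyond those the list of variables names. The downside is the assumption that loss depends only on observed VAS, which is why the sensitivity analysis is needed.

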Regarding the use of US-PICT, there are multiple studies that support this practice. They recognize it as "an effective and safe treatment in CT, since it produces a significant clinical and radiological improvement"(7). A study carried out in the year 2022, which retrospectively sought to study the results of this technique, culminated demonstrating a significant improvement in pain in patients treated with this technique (11).

Few studies have been conducted to determine which type of therapy is most effective in each case, with very mixed conclusions. In the 2014 systemic review by Louwerens et al, it was shown that both the use of high-energy ESWT and US-PICT are effective treatments in chronic cases of TC for patients with symptomatology longer than 6 months, however it gave greater effectiveness to ESWT.(12) However, [name] et al, in 2014 published a randomized study which concluded that "ultrasound-guided needling treatment was more effective in restoring function and short-term pain relief." (13)

The aim and desire of this study goes a bit further and is outlined below.

3. Main and secondary objectives

1. Main objective:

- The main objective is to compare the mean differences in VAS at 1 month, 3 months and 6 months according to the treatment received, US-PICT or ESWT in patients with TC according to the evolutionary stage of the lesion based on the Bianchi Martinoli classification.

2. Secondary objectives:

- To know if there are variations in functionality with the Latinen test, joint balance (ROM), PGI and CGI.
- To protocolize an attitude towards this type of pathology.
- To favor the use of hospital resources.

4. Design of the study

Design: We propose to conduct a **prospective experimental longitudinal analytical block randomized clinical trial**.

Study population, variables and inclusion-exclusion criteria.

Inclusion criteria:

- Patients aged 30 - 60 years.
- Omoalgia lasting more than 3 months.

- Radiographic and ultrasound visualization in both planes of calcification.
- Sizes > 5 millimeters (mm).

Exclusion criteria:

- Patients not meeting inclusion criteria.
- Presence of another evident cause of pain (joint degeneration, capsulitis, rotator cuff tendon ruptures...).
- Patient who has previously received ESWT or US-PICT.
- Contraindication of therapies: infection, drug allergies, cancer....

Variables to take into account:

- Age: years
- Sex: male/female
- Type of therapy: ESWT/barbectomy

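### The VAS comparison uses baseline VAS only by subtraction; a baseline-adjusted ANCOVA within each lesion type would be a cheap gain in precision in most assumed scenarios

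*Combined protocol and SAP*

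**What the plan says.** The analysis plan is the 3rd Phase of the work plan in section 4. It is a general menu of tests sorted by design. For independent data it gives "2 groups: Student's t-test or Mann-Whitney U-test" and "More than 2 groups: Analysis of variance or Kruskal-Wallis"; for paired data it gives the paired t-test or Wilcoxon, and repeated-measures ANOVA or Friedman.

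Baseline VAS enters through one derived variable: "A new variable VAS difference (VASDIF) will be created later, with the data obtained, according to the following formula". The formula is initial VAS minus VAS at month x, and its stated purpose is "in order to evaluate the variation with the initial VAS levels". The comparison is then given as "Variable agrupadora: ESWT Vs US-PICT", with type I and type II/III calcifications set out beneath it. The menu does not say which test is applied to VASDIF.

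The main objective in section 3 asks for the treatment comparison "according to the evolutionary stage of the lesion based on the Bianchi Martinoli classification". The 1st Phase allocates by "stratifying according to the Bianchi Martinoli classification: (I/II or III"), and its table shows 14 patients per treatment in type I and 14 in type II/III. The list of variables has VAS recorded "initial, at 1, 3 and 6 months".

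**The concern.** A change score fixes the coefficient of baseline VAS at 1. ANCOVA estimates that coefficient from the data, so it has smaller error variance than the change score unless the true slope is close to 1, apart from a small cost for estimating the slope. Baseline VAS is already recorded, yet no model named in the readable text uses it as a covariate. Repeated-measures ANOVA, listed for paired data, could carry initial VAS as a time level, but that is not covariate adjustment, and no group-by-time model is specified.

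At stake is the width of the confidence interval for the treatment difference within each lesion type. With 14 per arm at entry and about 11 after losses, each of these comparisons is small.

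**Working it through.** **Inputs from the documents.** Target difference 3 VAS points, SD 5 (not stated whether of a single VAS value or of VASDIF), two-sided alpha 0.05, beta 0.2, 28 per arm, 20% loss (Sample size); 14 per cell (1st Phase table). After losses: 14 × 0.8 = 11.2, taken as 11.

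**Assumed.** Baseline to follow-up correlation r = 0.3, 0.5 or 0.7; ratio of follow-up SD to baseline SD k = 1, 1.25 or 1.5. The documents give neither.

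**The plan's own figure.** The plan gives none for baseline adjustment. Its 28 per arm does not reproduce with the two-arm, two-sided formula at difference 3 and SD 5, which gives 44 per arm, or 44/0.8 = 55 with losses. That is a separate matter, and nothing below depends on it.

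**Step 1, variances.** With baseline SD s:
- Var(VASDIF) = s²(1 + k² − 2rk)
- residual variance of ANCOVA = k²s²(1 − r²)
- cost of estimating the slope in one lesion type with n per arm: factor 1 + 1/(2n − 4), which is 1.056 at n = 11 and 1.042 at n = 14.

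Example, k = 1 and r = 0.5: 0.75/1.00 = 0.750; 0.750 × 1.056 = 0.792, a 21% reduction.

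**Step 2, variance of the separate ANCOVA relative to VASDIF, 11 per arm.**

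| k | r = 0.3 | r = 0.5 | r = 0.7 |
|---|---|---|---|
| 1 | 0.686 (-31%) | 0.792 (-21%) | 0.897 (-10%) |
| 1.25 | 0.828 (-17%) | 0.942 (-6%) | 1.035 (+4%) |
| 1.5 | 0.920 (-8%) | 1.018 (+2%) | 1.053 (+5%) |

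**Step 3, interval half-width at 11 per arm, if SD 5 is the SD of VASDIF.**
- Unadjusted: t(20) = 2.086; 2.086 × √(2/11) × 5 = 4.4.
- Separate ANCOVA: t(19) = 2.093; 2.093 × √(2/11) × 5 × √ratio = 3.7 (ratio 0.686) to 4.6 (ratio 1.053).

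**Step 4, power for 3 points (noncentral t), same SD assumption.**
- 11 per arm: 26.8% unadjusted; 25.6% to 36.5% with separate ANCOVA.
- 14 per arm: 33.3% unadjusted; 32.2% to 45.8% with separate ANCOVA.
- At each size, power is slightly below unadjusted in 3 of the 9 scenarios: k = 1.25 with r = 0.7, and k = 1.5 with r = 0.5 or 0.7.

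**Step 5, why the fits should be separate.** One model for both types, with a treatment-by-type term, assumes a common baseline slope and a common residual variance. Simulation with no treatment effect at 11 per cell gives these type I errors within the two types (less variable type first):

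| SD ratio of the types | Joint model | Separate fits |
|---|---|---|
| 1:1.25 | about 3% and 7% | about 5% each |
| 1:1.5 | about 1.5% and 9% | about 5% each |

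**The case against.** The strongest reply is that this is a preference for efficiency and not an error. The starting hypothesis and the main objective are both framed as differences in VAS, VASDIF measures just that, and a t-test on it is valid under randomisation. That stands. A reader might infer that the planned comparison is biased; the documents do not support this. Chance baseline imbalance is not a second harm either. Its 95% limit, 1.96 × √(2/n), is 0.74 baseline SD at 14 per arm and 0.84 at 11, but the unadjusted interval already allows for it. This argument assumes random allocation. The wording that ties a patient's treatment to that of the previous patient is a separate point.

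A second reply is that the gain is uncertain. That also stands: r and k are assumed, and in some scenarios adjustment costs a little. A reader might infer that adjustment would rescue the study's power, or that low power supports this point. Neither follows. The low power rests on reading SD 5 as the SD of VASDIF. With an assumed baseline SD of 2 and r = 0.5, the SD of VASDIF would be 2.0 (k = 1) to 2.3 (k = 1.25), and the unadjusted half-width at 11 per arm only 1.8 to 2.0.

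A third reply is that a joint model would look better still. Part of its apparent gain comes from pooling the error across lesion types (39 degrees of freedom against 20) and not from baseline adjustment, and its error rates suffer if the types differ in variability.

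Finally, a reader might infer that the plan excludes any adjusted analysis. Two figures in the 3rd Phase are not shown, so the absence can be claimed for the readable text only. Nothing in that text points to an adjusted model.

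**Conclusion.** The point holds as a cheap improvement in precision, not as a bias or a fault in validity. For ESWT against US-PICT the readable plan names only unadjusted tests and uses baseline VAS only by subtraction. At 11 per arm, a separate ANCOVA in each lesion type would change the variance by between -31% and +5% over the assumed r and k, with a reduction in 6 of the 9 scenarios. The downside is one degree of freedom and up to about 5% more variance, when follow-up VAS is much more variable than baseline and r is high. The power and half-width figures also require SD 5 to be the SD of VASDIF, which the Sample size section does not state. Adjustment does not repair the sample size.

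**What to change.** In the 3rd Phase, state that the main VAS analysis within each lesion type (I; II/III) is an ANCOVA of follow-up VAS on treatment and baseline VAS, fitted separately by type, reporting the adjusted treatment difference with its 95% confidence interval. Keep the t-test or Mann-Whitney on VASDIF as a sensitivity analysis. If a joint model with treatment-by-type is wanted, make it secondary and state that it assumes a common slope and residual variance.

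The cost is a few sentences and slightly more work in the SPSS software already planned. The 6-month model needs no new data, because the table of variables shows VAS at the initial consultation and at 6 months. The list of variables also has VAS at 1 and 3 months, but the table as extracted does not show it there. Confirm that collection before applying the model at those visits.

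### No adverse-event or complication item is among the data to be collected, so a randomized comparison of an invasive with a non-invasive treatment would report no harms

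*Combined protocol and SAP*

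**What the plan says.** Section 4 (Work plan, 1st Phase) defines the data: "The variables indicated above and in the table of variables will be collected from these patients". The list under the variables heading in section 4 covers age, sex, therapy, endocrine and rheumatologic disease, calcification features, previous treatment, ROM, VAS, Latineen, PGI-I and CGI. At the follow-up reviews, "the variables will be taken again as indicated in the table of variables" (2nd Phase). The 3rd Phase gives "Main variables: VAS, Test de Latineen y variables, PGI y CGI".

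The secondary outcome objective in section 3 is "To know if there are variations in functionality with the Latinen test, joint balance (ROM), PGI and CGI". Another secondary objective is "To protocolize an attitude towards this type of pathology".

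The treatments differ in kind and in number of contacts. US-PICT is one session with a suprascapular nerve block (corticosteroid and bupivacaine), lidocaine infiltration of the calcification and repeated aspiration. For ESWT, "The number of sessions will be between 4 - 8 according to the patient's clinical condition", with 5 to 10 days between sessions. Reviews in both arms are timed in the same way: "One at 1 month, 3 months and another at 6 months after the end of therapy".

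Two other places come near the subject. Ethical aspects makes a general commitment to good clinical practice. Resources required says that data come from the hospital's clinical database. Neither names a harm item, a way of asking about it, or an analysis of it.

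**The concern.** One treatment involves needles, a nerve block and injected drugs, and the other does not. Where the aim is to decide which to indicate and to write a protocol from the answer, harms belong in the comparison alongside pain and function. A harm variable that was never collected cannot be sensibly rebuilt at analysis.

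The fallback would be to search routine clinical notes afterwards. Staff see ESWT patients several more times than US-PICT patients during treatment, so an early, short-lived event has more chances to be noted in the ESWT arm. A count from the notes would then partly reflect attendance.

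**Working it through.** **1. Is there a harm item anywhere?** Each place that could hold one:

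| Place | Harm item? |
|---|---|
| Section 3, main and secondary objectives | none |
| Section 4, variable list | none |
| Section 4, table of variables | none in the text as read |
| 3rd Phase, main variables and tests | none |
| Ethical aspects; Resources required | general statements only |

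The table may be damaged: it shows no VAS at 1 and 3 months, although the variable list requires it. The finding does not depend on the table, because the list, the objectives and the main-variables line agree. The main-variables line alone would be weak evidence, since it also omits ROM, which is collected. The firmest evidence is the 1st Phase sentence that defines what is collected, read with the list.

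**2. Contacts by arm.** Inputs from the Work plan: 1 US-PICT session; 4 to 8 ESWT sessions, 5 to 10 days apart; 3 reviews in each arm.

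- US-PICT attendances from the start of treatment: 1 + 3 = 4.
- ESWT attendances: 4 + 3 = 7 to 8 + 3 = 11.
- The excess of 3 to 7 consists entirely of treatment sessions.
- Next planned contact after the first treatment: about 5 to 10 days (ESWT) versus about 30 days (US-PICT).

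**3. Time from first treatment to each review.** Take 1 month as 30 days and 6 months as 180 days. ESWT duration is (sessions − 1) × gap.

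- Shortest: (4 − 1) × 5 = 15 days. Longest: (8 − 1) × 10 = 70 days.
- First review: US-PICT about day 30; ESWT about day 15 + 30 = 45 to 70 + 30 = 100.
- Last review: US-PICT about day 180; ESWT about day 15 + 180 = 195 to 70 + 180 = 250.

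A question about any event since first treatment would therefore span a longer period in the ESWT arm at every review. The first 180 days after the first session are covered by the last review in both arms.

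**4. What the planned numbers could show.** The plan gives no figure on harms to reproduce. I take its 28 per arm as stated; whether 28 suits the VAS comparison is a separate matter. If 28 is the number enrolled, 20% loss leaves 28 × 0.8 = 22.4, about 22.

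With zero events, the upper exact two-sided 95% limit is 1 − 0.025^(1/n):

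- n = 28: 12.3%
- n = 22: 15.4%

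The documents give no event rates, so the following rest on assumed rates.

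- Chance of seeing at least one event at a true rate of 5%: 1 − 0.95^28 = 76%; 1 − 0.95^22 = 68%.
- Power to separate 5% from 20% with 28 per arm, two-sided 0.05, normal approximation. The pooled standard error is √(2 × 0.125 × 0.875 / 28) = 0.0884 and the unpooled is √((0.05 × 0.95 + 0.20 × 0.80) / 28) = 0.0861. Then z = (0.15 − 1.96 × 0.0884) / 0.0861 = −0.27, giving about 39%.

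**The case against.** The strongest reply is that the trial commits to good clinical practice and draws on a clinical database, so complications would be seen and noted in ordinary care; that pain scores at 1, 3 and 6 months would show lasting worsening; and that with 28 per arm no useful comparison of harms is possible anyway.

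Part of this stands. The numbers support description only. VAS, Latineen and ROM could show persistent deterioration, though not its cause, nor an event that resolved before the review. Removed consent pages may describe risks, but would not normally create a collected variable. The general statements do not define an event, a question, a time window or a summary by arm, so the omission remains.

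Several stronger readings are tempting and are not supported:

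- A reader might infer that a first review at 1 month makes detection unequal. That timing applies to both arms. The imbalance comes from the number of treatment sessions, and it matters only if informally noted events are later retrieved, which the plan does not say it will do.
- A reader might infer that the protocol names its own treatment risks. It lists "Contraindication of therapies: infection, drug allergies, cancer" as contraindications, and capsulitis and tendon rupture as other causes of pain. It calls none of them a complication of treatment.
- A reader might infer that the global scales, shown only at 6 months, would miss early deterioration. That rests on a table that may be damaged.
- A reader might infer that the choice of treatment would rest on benefit alone. Use of hospital resources is also a stated objective.
- A reader might infer that harms would go unrecognised in care. The documents show only that they are not trial data.

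**Conclusion.** The point holds as an omission from data collection. As written, the trial would report no harms by arm, and a treatment protocol drawn from it would lack that side of the comparison. Later retrieval from records is possible but not like for like, given 1 versus 4 to 8 treatment contacts.

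The consequence is moderate. The VAS comparison is untouched. Adding the item would allow a descriptive statement, not a powered test: with no events, rates above roughly 12% to 15% per arm would be excluded. The conclusion assumes that the variable list is complete as read, that months are 30 days, and, for the 22, that the 20% loss comes out of the 28.

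**What to change.** Amend section 4 as follows.

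- **Variable.** Add an adverse-event/complication variable to the variable list and to the 1-, 3- and 6-month columns of the table. Ask the same structured question in both arms, recording event type, onset date and outcome.
- **Window.** Use onset dates to restrict the between-arm summary to one fixed window from the first treatment session that both arms complete, for example the first 180 days. Apply the same window to any check of the clinical database.
- **Analysis.** Report it as a descriptive secondary outcome by allocated arm: number, percentage with its denominator, and exact two-sided 95% confidence interval. State that no powered comparison is intended.

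The cost is a short amendment, one form section and a few minutes at existing visits. No extra patients, visits or procedures are needed. There will be some recall error. Onset dates equalise the window but not the recall period, which at the first review is about 45 to 100 days for ESWT and about 30 for US-PICT. If enrolment has begun, the question can still be added at the remaining reviews.
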